- 4. Predictive effect of cardiac biomarkers (terminal pro-B-type natriuretic peptide (NTproBNP, D-dimer, C-reactive protein (CRP), high-sensitivity troponin (hsTn)) for CV events
- 5. Percentage of participants with ISRs at each visit during the 168 days treatment period

Note: Photography of injection sites will be performed at each dosing visit, and ISRs will be scored based on a specific scoring matrix.

Statistical Methods

Analysis Populations

Screening population: All participants who signed the informed consent form.

Safety population: All participants who received any dose of the IMP. *Intention-to-treat (ITT) analysis set:* All participants included in the safety population for whom the primary endpoint is evaluable.

Per protocol (PP) analysis set: All participants included in the ITT analysis set who complete the study without major protocol violation.

The analysis will be done in 2 stages. Stage 1 will only include the analysis of the primary objective, which investigates the effect of the loading dose required to achieve castration levels by Day 28. Stage 2 will include all other analyses.

The primary objective will be assessed by determination of the proportion of participants achieving castration level T concentrations on Day 28.

The primary result will be the proportion of those participants in the PP analysis set, together with its Clopper-Pearson confidence interval (CI) and absolute frequencies. The same holds for the proportion of participants maintaining castration over 24 weeks at all scheduled visits.

In addition the calculation of the Kaplan-Meier estimate of the proportion of patients who achieve and maintain castrate T levels (T level < 50 ng/dL) from Day 28 through the end of the treatment period will be done.

All safety and efficacy endpoints will be summarised descriptively, i.e. by absolute and relative frequencies (relative to the respective analysis

ANT-1111-02, Teverelix TFA in Prostate Cancer FINAL Version 5.0, 31 May 2022 Page 14 of 84

population) for categorical endpoints. The distribution of continuous endpoints will be described by standard measures of location and dispersion in terms of mean, standard deviation (SD), median, Quartiles 1 and 3, minimum and maximum, and CIs for the mean.

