#### **4.1.3      Supplementary FDA Recommended Efficacy Measure**

Supplementary analysis will be conducted utilizing the Kaplan-Meier technique to estimate the proportion of patients who achieve and maintain castrate T levels (<0.5 ng/mL or 1.73 nmol/L) from Day 28 through the end of the treatment period.

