#### 5.1.2 Default Descriptive Statistics and Data Rules

In general, all continuous measures will be summarised descriptively, including number of available values, mean, standard deviation (SD), median, 1st quartile (for primary and secondary efficacy measures), 3rd quartile (for primary and secondary efficacy measures), minimum, maximum, and 95% confidence interval (CI) for the mean (for primary and secondary efficacy measures) if appropriate. Minimum and maximum values will be presented to the same decimal precision as the raw values, the 1st quartile, median, mean, 3rd quartile and 95% CI to one more, and the standard deviation, to two more decimal places than the raw values. Ordinal ratings may be handled as continuous data if appropriate.

Categorical data will be presented by frequency and percentage. All percentages will be presented to one decimal place except for values of 100%.

For AEs reported on a per-subject basis, medical history and concomitant medications, the denominator for the percentage calculation will be the number of subjects in each treatment arm. A subject will be considered at risk if the subject is in the Safety/FAS analysis set and entered the respective study period.

Unless otherwise specified, if reporting by visit, percentages are calculated using the number of subjects in the corresponding treatment group with non-missing data at that visit as the denominator, and if reporting overall, the denominator is the number of subjects in the given treatment group and population.

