### 5.3 Handling of Missing Data

#### 5.3.1 Efficacy Endpoints

Missing efficacy data will not be replaced.

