### 6.8.2 Secondary Efficacy Analyses

1. Proportion of participants achieving castration level with serum T <0.2 ng/mL or 0.6394 nmol/L at Day 28 will be analysed as mentioned in the Section 5.1.2 for both ITT and PP Population.
2. Proportion of participants achieving castration level with serum T <0.5 ng/mL or 1.73 nmol/L at Day 42 will be analysed as mentioned in the Section 5.1.2 for both ITT and PP Population.
3. Proportion of participants achieving castration level with serum T <0.2 ng/mL or 0.6394 nmol/L at Day 42 will be analysed as mentioned in the Section 5.1.2 for both ITT and PP Population.

---

Document:

C:\ProgramData\activePDF\Temp\DocConverter\API\Input\\$651f4dc0b253\$FE3041C5883446E892B20AB6D3F0E1BD.docx

Author: [name]

Version and Date: Version 1.0, 21 Apr 2023

Page 59 of 66

4. Proportion of participants achieving castration level with serum T <0.5 ng/mL or 1.73 nmol/L across treatment period from Day 28 until Day 168 will be analysed as mentioned in the Section 5.1.2 for both ITT and PP population.

*Note: Castration level is defined as the observed percentage of participants who have T concentrations <0.5 ng/mL (1.73 nmol/L) at all scheduled visits.*

Descriptive statistics with proportion, its Clopper-Pearson confidence interval (CI) and absolute frequencies.

5. Proportion of participants achieving castration level with serum T <0.2 ng/mL or 0.6394 nmol/L across treatment period from Day 28 until Day 168 will be analysed as mentioned in Section 5.1.2 for both ITT and PP population.

6. Time to T levels falling below castration level (<0.5 ng/mL [1.73 nmol/L]) for the first time. First time castrate serum level (<0.5 ng/mL [1.73 nmol/L]) will be defined as the analysis event. Analysis will be done from Day 1 to the end of the study.

The following censoring rules will be used for this analysis:

- Patients who did not achieve castrate serum T levels with central lab during the study period will be censored at their last serum T level assessment.
- Patients who leave the trial without achieving castrate serum T levels will be censored at their last serum T level assessment.

7. Time to (first) overstep of T castration level after achieving castration will be analysed using the Kaplan-Meier method.

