#### **6.8.3      Supplementary FDA Recommended Efficacy Analyses**

Supplementary analysis will be conducted utilizing the Kaplan-Meier technique to estimate the proportion of patients who achieve and maintain castrate T levels (<0.5 ng/mL or 1.73 nmol/L) from Day 28 through the end of the treatment period using the ITT population.

Treatment failure [non-castrate serum T levels ( $\geq 0.5$  ng/mL or 1.73 nmol/L) with central lab] will be defined as the analysis event.

The following patients will be considered as experiencing an event

1. Patients who did not achieve castrate serum T levels (<0.5 ng/mL or 1.73 nmol/L) by Day 28. Day 28 will be considered as the day of event.
2. Patients who successfully achieve a castrate serum T level by Day 28 but fail to maintain it throughout the treatment period. Day of failure (day of sampling) will be considered as the day of event.

---

Document:

C:\ProgramData\activePDF\Temp\DocConverter\API\Input\\$651f4dc0b253\$FE3041C5883446E892B20AB6D3F0E1BD.docx

Author: [name]

Version and Date: Version 1.0, 21 Apr 2023

Page 62 of 66

The following patients will not be considered as having experienced an event:

[figure not shown]
- 1 Patients who achieve and maintain castrate serum T levels with central lab from Day 28 through the end of the treatment period.
- 2 Patients who leave the trial for reasons other than a non-castrate serum T levels.

Censoring and handling of missing data rules will be used for this analysis:

[figure not shown]
- 1 Patients who achieve and maintain castrate serum T levels with central lab from Day 28 through the end of the treatment period will be censored at their last serum T level assessment.
- 2 Patients who leave the trial for reasons other than a non-castrate serum T level will be censored at their last serum T level assessment.
- 3 Patients with one or more consecutive missing serum T levels and a non-castrate serum T level after the missing time point(s) will be considered to have had an event (treatment failure) at the first missing time point. For example: if the subject's data is missing for Days 28 and 35 and having a non - castrate T levels ( $\geq 0.5$  ng/mL) on Day 42 we should consider that the subjects had an event on day 28.

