- 4 Patients with castrate serum T levels immediately before and after a single missing serum T level will not be considered to have had an event (treatment failure) at the missing time point. For example: if the subjects have castrate T levels ( $<0.5$  ng/mL) for Days 28 and 42 but data on day 35 is missing will not be considered to have had an event on day 35.

- 5 Patients with two or more consecutive missing serum T levels and castrate serum T levels immediately before and after the missing time points will be censored at their last T level before the missing data. For example: if the subjects have missing castrate T levels ( $<0.5$  ng/mL) for Days 35, 42 but have data on day 28 and 84 the data on Day 28 will be censored.

Time to event will be calculated as: **(date of event - date of Day 28) + 1**.

The presentation of the results will include the median by Kaplan-Meier function, 95% CI for Kaplan-Meier median and the Kaplan-Meier survival curve. The proportion of participants achieving castration level with serum T  $<0.5$  ng/mL or 1.73 nmol/L across the treatment period from Day 28

Document:

C:\ProgramData\activePDF\Temp\DocConverter\API\Input\\$651f4dc0b253\$FE3041C5883446E892B20AB6D3F0E1BD.docx

Author: [name]

Version and Date: Version 1.0, 21 Apr 2023

Page 63 of 66

to Day 168, along with Clopper-Pearson CI of the proportion will be presented for both ITT and PP Population at each assessment point.

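### The FDA-recommended Kaplan-Meier analysis lists a median but no Day 168 Kaplan-Meier probability with a CI, and rule 3's Day 28 example cannot occur in its ITT population

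*SAP*

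**What the plan says.** The aim is consistent across the documents. The Statistical Methods part of the protocol synopsis promises "calculation of the Kaplan-Meier estimate of the proportion of patients who achieve and maintain castrate T levels". SAP 4.1.3 describes the supplementary analysis as "utilizing the Kaplan-Meier technique to estimate the proportion of patients who achieve and maintain castrate T levels", and SAP 6.8.3 specifies it "from Day 28 through the end of the treatment period using the ITT population".

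The outputs are given at the end of SAP 6.8.3: "The presentation of the results will include the median by Kaplan-Meier function, 95% CI for Kaplan-Meier median and the Kaplan-Meier survival curve". The next sentence adds the Day 28 to Day 168 proportion below 0.5 ng/mL, "along with Clopper-Pearson CI of the proportion will be presented for both ITT and PP Population at each assessment point". SAP 6.8.2 item 4 treats that proportion as a secondary endpoint, "defined as the observed percentage of participants who have T concentrations <0.5 ng/mL (1.73 nmol/L) at all scheduled visits". SAP 5.3.1 adds: "Missing efficacy data will not be replaced".

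SAP 6.8.3 also has its own rules for censoring and gaps. Rule 3 makes a man with missing values followed by a non-castrate value an event at the first missing time point. Its worked example has Days 28 and 35 missing, Day 42 non-castrate, and the event placed on Day 28. SAP 3.4 admits to the ITT set only dosed participants with a central-laboratory testosterone at Day 28.

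**The concern.** There are two separate gaps.

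**Output.** The quantity the analysis exists to estimate has no listed numeric estimate with a matching CI. A median time to loss of castration exists only if the curve falls to 50%, which a useful regimen should not allow. The one listed interval that looks like an answer, the Clopper-Pearson one, belongs to an observed percentage that does not use the section's censoring rules and whose denominator can be read in two ways.

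**Population.** Rule 3's example describes a failure the SAP says to count, but the ITT definition removes that man before the rule can apply. The first sensitivity analysis changes only the definition of failure, and the second again requires a Day 28 value. Failures of this kind are therefore left out of all three analyses, in unknown number.

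**Working it through.** **Inputs.** Protocol 8.1.12 plans 50 evaluable men in Group 2 from 60 enrolled at 16% dropout: 50/(1 − 0.16) = 59.5, so 60, which reproduces. SAP 6.8.3 states no expected result, and neither document gives a maintenance rate, so a range is assumed below. The 74.5% row borrows the null Day 28 response rate of Protocol 8.1.12 as a pessimistic marker; it is not a maintenance rate.

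**1. Will the median be reached?** Without censoring, it is reached only if at least half of the men fail. With true maintenance rate s, the chance is P(Bin(n, 1 − s) ≥ n/2).

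| s | n = 50 (≥25 fail) | n = 60 (≥30 fail) |
|---|---|---|
| 74.5% | 0.0002 | 0.00004 |
| 70% | 0.002 | 0.0009 |
| 65% | 0.02 | 0.012 |
| 60% | 0.10 | 0.075 |
| 55% | 0.28 | 0.26 |

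At 70% or better the median and its CI will almost certainly be reported as not reached.

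**2. Does the Clopper-Pearson proportion fill the gap?** Assumed data: 50 men, 3 events at the first time point, 1 at the next, then 8 censored for other reasons, then 1 event. This leaves 50 − 5 − 8 = 37 men observed castrate throughout.

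- Kaplan-Meier: S = (47/50) × (46/47) × (37/38) = 0.8958.
- Greenwood sum: 3/(50×47) + 1/(47×46) + 1/(38×37) = 0.002450, square root 0.0495.
- Log-log standard error: 0.0495/|ln 0.8958| = 0.4498. Limits: 0.8958^exp(±1.96 × 0.4498), giving 76.7% to 95.5%.
- Binomial, all 50 as denominator: 37/50 = 74.0% (59.7 to 85.4).
- Binomial, censored men left out: 37/42 = 88.1% (74.4 to 96.0).

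The same data give 89.6%, 74.0% or 88.1%. SAP 5.1.2 does not settle the denominator. For by-visit reporting, "percentages are calculated using the number of subjects in the corresponding treatment group with non-missing data at that visit as the denominator"; for overall reporting it uses the whole population. A proportion across the treatment period, shown at each assessment point, fits either default.

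**3. Rule 3 against the population.**

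| Text | Day 28 central testosterone |
|---|---|
| Rule 3 example (6.8.3) | Missing; event on Day 28 |
| ITT set (3.4), used for the main analysis | Required |
| First sensitivity analysis | Population unchanged, so required |
| Second sensitivity analysis | Required |

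The example cannot occur in any of them. Rule 3 still works for gaps that start after Day 28. SAP 6.8 says that men who miss the Day 28 visit should preferably not count as non-responders, but it says so only for the primary response rate.

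**4. What would restoring these men do?** Add f Day 28 failures and c men castrate and followed to Day 168 to the illustration. The risk sets become (50+f+c) with 3+f events, (47+c) with 1, and (38+c) with 1.

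| f | c | Kaplan-Meier at Day 168 |
|---|---|---|
| 0 | 0 | 89.6% |
| 1 | 0 | 87.8% |
| 2 | 0 | 86.1% |
| 0 | 2 | 90.0% |
| 1 | 2 | 88.3% |
| 2 | 2 | 86.7% |

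The estimate can move either way.

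**The case against.** The best defence is that the Kaplan-Meier proportion is already committed to as the aim in both documents, that the output sentence says what results will include and need not be exhaustive, that the curve displays the estimate, and that table content sits in output shells that are not available here. This stands as a limit on the claim: what is shown is a gap in the SAP text, not that the number will go unreported. It does not remove the gap, because the SAP specifies a CI for the median and none for its target.

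On the denominator, SAP 5.1.2 does supply defaults, and reporting at each assessment point leans towards the by-visit one. But the same sentence speaks of the whole treatment period, so the ambiguity remains. With censored men excluded, the binomial figure is only 1.5 points from Kaplan-Meier; the wide gap needs all 50 as denominator.

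On rule 3, an example does not redefine a population, so a strict reading simply excludes these men. The pattern is probably uncommon, since it needs two consecutive missing central values and then a Day 42 result. Both points are fair, and they are why correcting the example alone would be an acceptable remedy. The text still says to count a failure that the population excludes.

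The illustration is invented, and 50 is the planned per-protocol size, whereas this analysis uses ITT, which could be as large as 60. The n = 60 column leads to the same conclusion. The analysis is supplementary, and its first sensitivity analysis already counts leavers and gaps of two or more visits as failures.

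**Conclusion.** Both points hold. As written, SAP 6.8.3 lists a summary that will very probably be uninformative (chance of reaching the median 0.002 with 50 men and 0.0009 with 60, at 70% maintenance without censoring) and no Day 168 Kaplan-Meier probability with a CI. The interval offered beside it is for a different quantity, which in the assumed example lies 1.5 to 15.6 points below the Kaplan-Meier estimate depending on the denominator. Rule 3's worked example is incompatible with the ITT set and with both sensitivity analyses; the number of men affected is unknown and the direction of the net effect is not determined. The maintenance rates, event counts and censoring pattern are assumptions. The primary endpoint is not affected. The change should be made, because this analysis was added after discussion with the FDA and its headline number should be fixed in advance.

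**What to change.** 1. Name as the main output the Kaplan-Meier probability of remaining castrate at Day 168 (nominal time 168 − 28 + 1 = 141), and at each scheduled central-testosterone visit, with a Greenwood log-log 95% CI. Keep the median as secondary.
2. State the denominator of the Clopper-Pearson proportion and how censored and withdrawn men are counted in it.
3. Reconcile rule 3 with the population in one of two ways.
   - (a) Add a main or sensitivity analysis on all dosed participants. Where the Day 28 visit is missing, use first dose date + 28 days as the origin. Keep men with no central testosterone from Day 28 onwards out of the Day 28 risk set: in the illustration, wrongly including 6 such men gives (53/56) × (46/47) × (37/38) = 90.2% instead of 89.6%. State how rule 5 treats a gap starting at Day 28. Under this option, a man castrate on Days 21 and 42 with Days 28 and 35 missing would be censored at Day 21, which is time (21 − 28) + 1 = −6, while rule 3 would make the non-castrate man with the same gap an event.
   - (b) Move the example to a gap after Day 28 and state that participants without a Day 28 central value are excluded.

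The cost is SAP wording and one changed output table, plus one extra run under option (a). No new data are needed.

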**Sensitivity Analyses on Supplementary FDA Recommended Efficacy Analyses**

Two sensitivity analysis will be performed. In the first sensitivity analysis the definition of treatment failures will be expanded and include following patients as treatment failures (patients with event):

1. Patients who did not achieve castrate serum T levels (<0.5 ng/mL or 1.73 nmol/L) by Day 28.
2. Patients who successfully achieve a castrate serum T level by Day 28 but fail to maintain it throughout the treatment period.
3. All the patients who leave the trial will be considered to have had an event at their last serum T level assessment.
4. Patients with two or more consecutive missing T levels (regardless of T levels before and after those missing time points). They will be considered to have had an event at the first missing time point.

In the second sensitivity analysis the ITT population will be changed to the population of patients who have received any dose of IMP and have a non-missing central lab serum T record at Day 28 except for patients who received concomitant medications and herbal supplements that could possibly affect T levels.

## **6.9 Safety Analyses**

All safety and efficacy endpoints will be summarised descriptively, i.e., by absolute and relative frequencies (relative to the respective analysis population) for categorical endpoints.

### **6.9.1 Exposure to Study Medication**

Exposure to Study Medication will include derived continuous and categorical variables. Categorical variables will be summarised by absolute counts (n) and percentages (%). Percentages will be based on the number of subjects with data.

### **6.9.2 Adverse Events**

All AEs will be coded by MedDRA terminology and summarised by preferred term (PT) and system organ class (SOC). Frequencies of AEs will be presented by absolute and relative frequencies to the number of participants experiencing an event and the number of events for each SOC and PT.

All AEs, serious AEs, TEAEs, serious TEAEs, treatment-related AEs will be summarised in a single output.

Separate summaries will be produced for serious AEs, TEAEs and treatment-related AEs (see Section 4.2.3 for treatment-related AE definition).

EuDRA CT serious AEs and EuDRA CT non-serious treatment-emergent AEs summaries will also be presented.

#### **6.9.2.1 Injection Site Reactions**

Pain, Tenderness, Erythema/Redness and Swelling and their grade will be summarised at each visit and overall, for Stage 1, Stage 2 and final assessments..

---

Document:

C:\ProgramData\activePDF\Temp\DocConverter\API\Input\\$651f4dc0b253\$FE3041C5883446E892B20AB6D3F0E1BD.docx

Author: [name]

Version and Date: Version 1.0, 21 Apr 2023

Page 64 of 66

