6.3.4 Injection Site Inspection

Each injection site will be visually inspected at each visit for local reactions such as pain, tenderness, erythema/redness and swelling. If the only reaction is induration, this should be indicated on the eCRF and reported as an AE. Any other local reactions will be graded according to the grades mentioned as specified in Table 10 [15] and reported as an AE. Upon complete resolution of an injection site reaction, injection site inspections of that injection site can cease

During the first administration of the injection, an injection site inspection (ISI) will be performed to ensure that the injection site is free from blemishes, tattoos, or other marks that may make subsequent ISIs difficult. ISIs will also be performed at 30 minutes, 4, 12, and 24 hours post-dose. The ISI will be performed at 30 minutes post-dose for all other IMP administration. ISRs will be reported as AEs.

At maintenance dose visits ALL injection sites must be inspected unless an injection site reaction has fully resolved (including induration). For example, at Day 42 the following injection sites should be inspected: D0 SC; D0 IM; D42 SC. And at Day 84 the injection sites for D0 SC; D0 IM; D42 SC; D84 SC should be inspected. Only when an injection site reaction (including induration) has fully resolved can inspection of that injection site stop.

Table 10: Food and Drug Administration Local Toxicity Scale

Local Reaction to	Mild	Moderate	Severe	Potentially
Injectable Product	(Grade 1)	(Grade 2)	(Grade 3)	Life-
				threatening (Grade 4)
Pain	Does not interfere with activity	Interferes with activity or repeated use of non-narcotic pain reliever	Prevents daily activity or repeated use of narcotic pain reliever	ER visit or hospitalisation
Tenderness	Mild pain to touch	Pain with movement	Significant pain at rest	ER visit or hospitalisation
Erythema/Redness ^a	2.5–5 cm	5.1–10 cm	>10 cm	Necrosis or exfoliative dermatitis
Swelling ^b	2.5–5 cm and does not interfere with activity	5.1–10 cm or interferes with activity	>10 cm or prevents daily activity	Necrosis

ER=emergency room

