8.1.5 Analysis of Safety Data

Safety Endpoints

1. Number of participants with treatment-emergent AEs (defined as any AE occurring or worsening following treatment), summarised by system organ class (SOC) and preferred term (PT)

Note: Occurrence of ISRs will be included.

- 2. Mean changes in vital signs, triplicate 12-lead ECGs and laboratory data parameters at each visit during the 168-day treatment period, compared to baseline
- 3. Continuous 24 hour 12-lead Holter ECG (subset of 30 Group 2 subjects only)
- 4. Percentage of participants with ISRs at each visit during the 168-day treatment period *Note:* Photography of injections sites with visible injection site reactions will be performed at each visit, and ISRs will be scored based on a specific scoring matrix

The treatment-emergent AEs (defined as any AE occurring or worsening with the same date or later than that of the first application of study treatment) will be coded using the most recent version of the Medical Dictionary for Regulatory Activities (MedDRA) available at the study start date. This version will be used throughout the entire study. Updates to MedDRA will not be applied afterwards. Frequency tables for the preferred terms will be compiled based on participants experiencing an AE and on the number of AEs. These frequency tables will take the SOC into consideration.

All reported AEs will be listed and ISRs will be summarised.

The vital sign, triplicate 12-lead ECG, and laboratory data parameters will be presented using descriptive statistics and shift-tables with respect to normal ranges for each visit including changes from baseline.

Concomitant diseases and medical history will also be coded using MedDRA. These data will be presented using frequency tables by SOC and PT.

Previous medication and concomitant medication will be coded using the Anatomical Therapeutic Chemical Classification (ATC) dictionary. Frequency tables will be compiled based on the coding for the medication.

8.1.6 **Missing Data**

Missing efficacy data will not be replaced in general.

If a laboratory reports concentrations as unquantifiable (too low), the value will be set to 0. Values for samples that are not technically evaluable will be set to missing.

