**4.2.5 Injection Site Inspection**

Each injection site will be visually inspected at each visit for local reactions such as pain, tenderness, erythema/redness and swelling. If the only reaction is induration, this should be indicated on the eCRF and reported as an AE. Any other local reactions will be graded according to the grades mentioned as specified in Table 13 and reported as an AE. Upon complete resolution of an injection site reaction, injection site inspections of that injection site can cease.

During the first administration of the injection, an injection site inspection (ISI) will be performed to ensure that the injection site is free from blemishes, tattoos, or other marks that may make subsequent ISIs difficult. ISIs will also be performed at 30 minutes, 4, 12- and 24-hours post-dose. The ISI will be performed at 30 minutes post-dose for all other IMP administration. ISRs will be reported as AEs.

At maintenance dose visits ALL injection sites must be inspected unless an injection site reaction has fully resolved (including induration). For example, at Day 42 the following injection sites should be inspected: D0 SC; D0 IM; D42 SC. And at Day 84 the injection sites for D0 SC; D0 IM; D42 SC; D84 SC should be inspected. Only when an injection site reaction (including induration) has fully resolved can inspection of that injection site stop.

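### The SAP's by-visit injection site summary covers only the four graded signs, so it does not deliver the protocol's by-visit ISR percentage and leaves out induration-only reactions

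*SAP*

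**What the plan says.** **Endpoint.** The protocol synopsis lists among the safety endpoints "Percentage of participants with ISRs at each visit during the 168 days treatment period". Protocol 8.1.5 repeats it: "Percentage of participants with ISRs at each visit during the 168-day treatment period". In both places a note adds that ISRs are to be scored on a scoring matrix. The SAP does not restate this endpoint.

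**What counts as an ISR.** Protocol 6.3.4 (Injection Site Inspection) names induration as part of the term: "Only when an injection site reaction (including induration) has fully resolved can inspection of that injection site stop". SAP 4.2.5 carries the same sentence.

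**How induration is recorded.** SAP 4.2.5, following the protocol, says: "If the only reaction is induration, this should be indicated on the eCRF and reported as an AE". It then says: "Any other local reactions will be graded according to the grades mentioned as specified in Table 13 and reported as an AE". Table 13 (Table 10 in the protocol) has four rows: pain, tenderness, erythema/redness and swelling. Induration has no row and so no grade.

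**What is summarised.** SAP 6.9.2.1 is one sentence: "Pain, Tenderness, Erythema/Redness and Swelling and their grade will be summarised at each visit and overall", for Stage 1, Stage 2 and the final assessments. The other route is the adverse event tables in SAP 6.9.2: "Frequencies of AEs will be presented by absolute and relative frequencies to the number of participants experiencing an event", by system organ class and preferred term.

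**The concern.** The endpoint asks a single question at each visit: what share of participants have an injection site reaction? The SAP answers a different one: how many have each of four signs, and at what grade? Two things go missing.

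- There is no per-participant percentage with any ISR.
- A reaction that consists of induration alone falls under none of the four signs, although both documents treat it as an ISR and require inspection to continue until it resolves.

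Local tolerability is a stated safety objective. The product is a depot given as two injections on Day 0 and then one on each of Days 42, 84, 126 and 168. Protocol 1.2.1 reports that injection site reactions limited the high doses in the repeat-dose animal studies, and protocol 1.2.2 puts mild ISRs among the most frequent clinical adverse events. A by-visit ISR rate is likely to be read closely, and a reader could take the four-sign table for it.

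**Working it through.** No figure in the plan can be reproduced here, because neither document gives an ISR or induration rate. The check sets the texts side by side.

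1. **Scope of the endpoint.** The protocol wording is ISRs, at each visit, per participant. It is not limited to graded reactions or to named signs.

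2. **Scope of the term.** Protocol 6.3.4 and SAP 4.2.5 both include induration in it.

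3. **Scope of the summary.** The four signs in SAP 6.9.2.1 are exactly the four rows of SAP Table 13. Induration is outside that table.

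4. **Can the endpoint be recovered from the four rows?** No, for two reasons.
   - The signs overlap within a participant. If p1 to p4 are the four percentages at a visit, the percentage with at least one graded sign lies between max(p1, p2, p3, p4) and min(100%, p1 + p2 + p3 + p4). The rows alone do not fix it.
   - Even the exact percentage with at least one graded sign leaves out the induration-only group. With N participants having data at the visit:
     - endpoint = (n with any graded sign + n with induration only) / N
     - shortfall if only graded signs are counted = n with induration only / N

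   The shortfall is zero or positive, so the direction is known. Its size is not, because the documents give no value for n with induration only. For scale, one such participant among the 60 planned for Group 2 is 1/60 = 1.7 percentage points at a visit where all 60 have data. This is the weight of one participant, not an estimate.

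5. **Do the adverse event tables fill the gap?** Only in part. Induration-only reactions must be reported as adverse events, so they reach the tables in SAP 6.9.2. No by-visit breakdown is stated there. SAP 4.2.3.1 counts repeated events of one preferred term once per subject, from the earliest start to the latest stop. Whether a reaction was present at a given visit is not shown.

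6. **Is the narrowing declared?** SAP 7.1 lists changes from the protocol analyses and does not mention it.

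7. **Can the missing rows be built?** The inspection text guarantees an eCRF entry for induration when it is the only reaction. That is enough for the any-ISR row, because a participant with induration plus another sign is already counted through that sign. It is not enough for a full present/absent row for induration, since the documents do not say that induration is recorded when other signs coexist.

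**The case against.** The best defence is the note attached to the endpoint. It says ISRs are scored on a matrix, the only matrix in the documents is the four-row toxicity scale, and the inspection text separates induration from the reactions that are graded. On that reading SAP 6.9.2.1 summarises what the endpoint intended. This gives a graded-only reading some support. It does not settle the matter: the note describes scoring, the endpoint itself says ISRs, and both documents put induration inside that term. Even a graded-only endpoint would need a percentage with any graded reaction, which 6.9.2.1 does not specify.

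Other points on that side:

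- SAP 6.9 opens with a general promise to summarise all safety endpoints by frequencies. True, but it does not say what counts as an ISR at a visit.
- Table layouts are in the output shells (SAP Attachment 1), which are not among the documents. They may carry the missing rows, so the finding concerns the SAP text only.
- Induration still appears in the adverse event tables and, under protocol 8.1.8, in the data listings. This stands: only the by-visit display is missing.

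A reader might infer more: that a planned ISR rate is biased downward by some stated amount, or that the duration of reactions is understated. The documents support neither. The SAP defines no any-ISR rate that could be biased; an undercount arises only if someone builds the rate from the four signs. Duration is not this endpoint, and onset and end dates are collected for every adverse event.

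**Conclusion.** The point holds as a gap between a stated safety endpoint and its planned summary. Followed as written, SAP 6.9.2.1 gives no by-visit percentage of participants with any ISR, and participants whose only reaction is induration appear in no by-visit ISR summary. The direction of any undercount is known and its size is not.

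The conclusion rests on reading ISR as both documents use the term, with induration included, and on the SAP text without the output shells. It does not touch any efficacy result. It is a minor point, worth making because the correction costs almost nothing.

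**What to change.** In SAP 6.9.2.1, add for each visit:

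- the number and percentage of participants with any ISR, defined as at least one of the four graded signs, or induration, at any injection site;
- the number and percentage with induration only, taken from the existing eCRF entry and counted where no graded sign is present at any site at that visit.

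Use participants with non-missing data at that visit as the denominator, which is already the by-visit default in SAP 5.1.2. With these definitions the induration-only group and the group with any graded sign do not overlap, so the two add up to the any-ISR row.

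If the endpoint is meant to cover graded reactions only, say so with a reason in SAP 7.1 and still give the percentage with any graded reaction.

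The cost is two extra rows in a planned table, a matching change to the shells if they lack them, and possibly a higher reported ISR rate. The assumption to confirm is that the induration entry is held by visit. SAP 7.2 rules out changes to Version 1.0 after database lock; after that point the rows can be added and explained in the study report.
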